1.1. Purpose

The primary objective of this randomized controlled trial is to examine the impact of a behavioral support intervention for adults with type 1 diabetes (T1D) who are starting on continuous glucose monitoring (CGM). This trial compares adults with T1D who are starting on CGM with behavioral supports (the intervention group) versus those who are starting on CGM without behavioral supports (the control group). We will examine group differences over a 3-month period on two sets of outcomes. The first set of outcomes includes glycemic variables (e.g. hemoglobin A1c, time in range). In this set of outcomes, A1c is the identified primary endpoint. The second set of outcomes includes psychosocial variables (e.g. diabetes distress, worry about hypoglycemia, technology attitudes), with diabetes distress as the primary endpoint. After the initial comparison of intervention to control across the first 3 months after starting CGM, we will conduct a longitudinal follow-up of glycemic and psychosocial outcomes at 6 and 12 months.

1.2. Background

1.2.1. Type 1 Diabetes (T1D) is a burdensome chronic disease; many adults with T1D do not meet treatment targets. The Centers for Disease Control and JDRF data estimate that there are over 1 million adults in the US with T1D (1, 2); 15,000 adults are newly diagnosed with T1D annually and by 2050 4.4 million adults in the US are expected to have T1D (1). T1D requires constant attention to glucose levels, food intake and physical activity, and insulin dosing decisions. Giving too much or too little insulin could result in hypo- or hyperglycemia, both of which carry risks of developing long-term complications. *National data show that the majority of adults do not meet ADA's recommended glycemic target of A1c<7.0% (86% of adults 18-25; 70% of adults over 25) (5).* Adults with T1D are well-positioned to benefit from behavioral interventions that are tailored for their unique needs and integrated into clinical care.

1.2.2. Existing and emerging diabetes technologies can dramatically improve health and reduce burden, but adoption rates are low. Diabetes technology offers major advances in diabetes management that reduce self-management burden and improve health outcomes and quality of life for individuals with T1D (6-8). These devices include continuous glucose monitoring (CGM) systems and insulin pumps. CGM technology provides in-the-moment information about glucose levels, including direction and speed of change. CGM reduces management burden by reducing the need for frequent finger sticks. CGM has been shown to be cost-effective (9) and to help adults improve both glycemic control and time spent in target glucose range without increasing risk of hypoglycemic episodes or diabetic ketoacidosis (10-12). Furthermore, improvements in CGM accuracy have enabled the crucial next step toward automating diabetes management with closed loop systems. Closed loop systems have shown the ability to reduce hypoglycemia and glucose variability and increase time in range (16-20). In addition, these systems decrease the mental burden of living with T1D (21-23). *To experience the benefits of current and future diabetes technologies adults with T1D must be willing to wear and maintain a CGM and insulin pump over time.* We know that currently, more than half (~62%) of individuals with T1D use insulin pumps in the US (5), while only 14% of adults with T1D currently use CGM. Further, a concerning proportion of adults (27%) quit CGM within the first year due to the daily burden of using the device (24). *Providing adults with T1D with the resources and tools to work through modifiable barriers could lead to continued CGM use and increased readiness for closed loop.*

Table 1. ADA 2018 Recommendations for CGM	
Current recommendation (CGM)...is a useful tool to lower A1C in adults with T1D.	State of the science A - Strong evidence
Robust diabetes education, training, support are required for optimal implementation and ongoing use.	E- Expert consensus or clinical experience (clinical trials needed) (ADA, 2018)

1.2.3. There is no official standard of care for CGM initiation. Table 1 presents CGM recommendations from ADA's 2018 Standards of Medical Care in Diabetes (42). ADA recommends that adults receive robust education, training, and support for CGM use (42); this recommendation comes from expert consensus and clinical experience. There is a need to develop high-quality, evidence-based behavioral interventions to provide recommended training and support. *If adults with T1D receive comprehensive education and support alongside CGM initiation, they may be more likely to use the devices and to experience short- and long-term health and quality of life benefits.* Given that CGM is becoming part of "usual care" for

people with T1D and is a component of closed loop systems, the next key step is to test interventions that provide additional resources and support for CGM uptake versus CGM alone.

1.2.4. The need for guided diabetes device 'onboarding'. To address the need for increased support for initiating diabetes devices, the overall objective of the proposed study is to provide adults with T1D with a tailored behavioral intervention using evidence-based strategies and tools to enable them to maximize benefit from CGM and increase readiness for closed-loop technology. According to the widely used Technology Acceptance Model (44), factors such as the technology's perceived usefulness and ease of use influence likelihood of using and benefitting from the technology. Therefore, our ONBOARD (*Overcoming Barriers & Obstacles to Adopting Diabetes Devices*) intervention package will prepare adults with T1D to use and benefit from CGM by 1) setting realistic expectations for the technology; 2) providing resources and problem-solving skills to work through barriers; 3) helping to highlight benefits of the technology; and 4) planning for potential issues that may arise in the future to prevent CGM discontinuation. This study addresses a major gap in the literature on what guidance and support adults with T1D need, beyond education, to benefit from advances in diabetes devices and to increase their readiness to adopt new diabetes technologies.

1.3. Preliminary Studies

The preliminary work described here focused on identifying modifiable barriers to diabetes device use, pinpointing targets for intervention, and highlighting links between intervention targets and important diabetes outcomes.

1.3.1. We found that non-users of CGM are younger, have higher A1c values, and more negative attitudes toward diabetes technology compared to CGM-users. Through an online survey of participants in the T1D Exchange Clinic Network, we collected data from 1,503 adults with T1D regarding their current device use and major barriers to using diabetes devices (54.7% women; mean age=35.3±14.8 years; mean diabetes duration=20.4±12.5 years; 70% using insulin pumps; 37% using CGM). On average, non-users of CGM were 5 years younger; had higher A1c values (.37% higher mean A1c); and reported more barriers to device use compared to CGM users (22).

Table 1. Top Barriers to Device Use (n=1503)

Barrier	% Yes
Hassle of wearing devices all of the time	47.3
Do not like having diabetes devices on my body	34.8
Do not like how diabetes devices look on my body	26
Nervous that the device might not work	20
Do not want to take more time from my day to manage diabetes	17.5
Nervous to rely on technology	17
Worries about what others will think about you	10.5
I do not like diabetes devices because people notice them and ask questions about them	10.4

1.3.2. Physical, data, social, and trust barriers interfere with CGM use. In the same survey, barriers to using diabetes devices (CGM and insulin pump) fell into several categories: 1) hassle/ burden of wearing devices on the body; 2) nervous to rely on the technology; 3) time burden of managing diabetes; and 4) devices drawing unwanted attention from others (Table 1). We conducted a follow-up survey of adults who had discontinued using diabetes devices to learn their reasons for discontinuation (Table 2). Rates of CGM discontinuation are considerably higher than pump discontinuation (5). After cost, issues with alarms, accuracy, discomfort and pain led to CGM discontinuation. *Our preliminary data highlight why many adults with T1D feel the negatives outweigh positives of CGM and stop using this beneficial technology.*

Table 2. "Why did you stop using your CGM?" (n=249)	
	% Yes
Cost of supplies	35.3
There were too many alarms	32.1
It wasn't accurate	30.1
Don't like diabetes devices on my body	29.7
Wearing a CGM took too much time and effort	28.9
It was uncomfortable or painful	28.1
Too hard to get it to work right	22.1
Cost of device	21.7
Made it hard for me to sleep	20.1
Didn't trust it	18.1

Survey data strongly support the ADA recommendation for robust support tailored to the commonly endorsed barriers to using CGM to promote increased uptake and sustained use of CGM and, eventually, closed loop systems.

1.3.3. Closed loop systems depend on CGM accuracy to gain user trust. Closed loop systems require wearing a CGM and an insulin pump and partially automate insulin delivery. Given the novelty of closed loop systems, we aimed to understand major factors that could influence willingness to trust and accept the potential risks of closed loop. I applied my expertise in qualitative research methods to analyze focus groups with participants in a closed loop system trial (n=32). Results showed that user expectations and trust shaped overall satisfaction with the system and likelihood of continued use. Specifically, overly high/unrealistic expectations contributed to increased negative evaluations of the system (3). Issues with CGM accuracy and intrusiveness of alerts hurt

user trust and decreased the likelihood that someone would opt to continue using the system (24). Relatedly, our extensive interviews with adults with T1D (n=113) highlighted that CGM accuracy was a major priority when considering closed loop system adoption (45), since accuracy of CGM determines the system's ability to improve glycemic control. *Our results highlight additional potential barriers and intervention targets to promote adoption and sustained use of CGM, and to increase readiness for using closed loop systems. Results demonstrate the investigator's strong ability to conduct qualitative research related to T1D experience.*

1.3.4. Interventions with problem-solving, motivational interviewing, and social learning components can improve psychosocial and health outcomes in adolescents and adults with diabetes. Multicomponent interventions are advantageous because they capitalize on effective pieces of existing, evidence-based interventions (46, 47). Multicomponent interventions that include motivational interviewing, problem-solving, and cognitive behavioral therapy have demonstrated ability to improve A1c in T1D (48-50). Extensive evidence supports the benefit of problem-solving interventions for diabetes management (51-57). Motivational interviewing has also proven to be effective in promoting positive behavior change in diabetes management (58-60). Finally, successful programs to improve psychosocial and health outcomes often incorporate a social component, whether through group delivery (61), an online forum (63), or involvement of a peer coach (64-68). While these strategies can be beneficial, another powerful tool, informed by social learning theory (69), is to incorporate videos of first-person stories that model how individuals worked through relevant problems (70, 71). For example, YourWay, an Internet-based, social learning and problem-solving program, helped adolescents with T1D work through psychosocial barriers to diabetes self-management (63). Through digital storytelling, YourWay presented participants with first-person "stories" of diabetes problem-solving, which can help individuals develop problem-solving skills and self-efficacy through "vicarious learning" (72, 73).

[figure not shown]
CHAPTER 2: STUDY PROTOCOL

2.1. Synopsis of study protocol

The primary objective of this randomized controlled trial is to examine the impact of a behavioral support intervention for adults with type 1 diabetes (T1D) who are starting on continuous glucose monitoring (CGM). This trial compares adults with T1D who are starting on CGM with behavioral supports (the intervention group) versus those who are starting on CGM without behavioral supports (the control group). We will examine group differences over a 3-month period on two sets of outcomes. The first set of outcomes includes glycemic variables (e.g. hemoglobin A1c, time in range). In this set of outcomes, A1c is the identified primary endpoint. The second set of outcomes includes psychosocial variables (e.g. diabetes distress, worry about hypoglycemia, technology attitudes), with diabetes distress as the primary endpoint. After the initial comparison of intervention to control across the first 3 months after starting CGM, we will conduct a longitudinal follow-up of glycemic and psychosocial outcomes at 6 and 12 months.

2.2. Study procedures

Participants will be recruited at Stanford University through a combination of in-clinic, in community locations and online through type 1 diabetes online communities. Eligible participants will be adults (ages 18-50) who have not been using CGM consistently (>5 days/week) for at least the past 6 months. Once identified in clinic or once someone has expressed interest in the study, study staff will approach potential participants to explain the study, determine eligibility, and obtain informed consent. All participants will complete their baseline visit remotely. This baseline visit will include 1) completing a hemoglobin A1c test kit that is mailed to them in advance; 2) completing a baseline assessment survey online via a secure site (REDCap) to obtain demographic and psychosocial data and 3) initiate use of CGM supplies. Participants will be given the choice of using Dexcom G6 or Libre 2 CGM. Participants will be mailed 12 weeks of CGM supplies of their choice and will receive initial standard CGM introduction and education from the study staff and will be provided with standard resources from the device manufacturer at this baseline visit. At baseline, participants will then be randomized. We will randomize at a 1:1 ratio, intervention to control. Those randomized to the intervention (ONBOARD) condition will schedule 4 60-minute sessions with study interventionist (every 2 weeks), with the first session scheduled for 2 weeks after CGM initiation. Sessions will be conducted via a secure, HIPAA-compliant, videoconferencing software (Zoom) and may be recorded to ensure consistency and quality of the intervention across participants and interventionists. Each participant will receive one unique Zoom link that they will use for all 4 of their study sessions. At the 3-, 6-, and 12-month time points, participants will be mailed A1c test kits for follow-up A1cs, and will complete a follow-up REDCap survey at these time points as well. The follow-up survey will assess psychosocial variables, technology satisfaction, and changes to demographic/medical information. Each follow-up survey is expected to take 30 minutes to complete. Of note, all study participants will

receive instruction on how to work with their insurance to obtain coverage for continuing to use CGM after the first 12 weeks of the study. At the 3-, 6-, and 12-month timepoints, CGM data downloads will be obtained.

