2.3. Study groups

There are two groups in this study: intervention (ONBOARD) and control (CGM-only). All participants will receive 12 weeks of CGM supplies and will receive standardized education about getting started with CGM. A person trained in delivering education about CGM will deliver education about CGM use and will be present during a virtual meeting while participant is inserting first sensor during training. This individual will be available to assist with questions from participants. In addition, Dexcom and Abbott representatives are available to participants for technical questions or issues with the system, just like the access any CGM user has. All participants in both groups will be required to actively use CGM for 12 weeks. After that time period, they can continue or discontinue use of CGM. If they decide to continue, the study team will provide information on working with insurance and with their provider to obtain CGM for both study groups.

After randomization, participants in the intervention group will receive 4 one-on-one sessions of ONBOARD (OvercomiNg Barriers & Obstacles to Adopting Diabetes Devices). Sessions will be held every 2-3 weeks over the 12-week period

when participants are using CGM provided by the study. ONBOARD is a multicomponent intervention to provide tailored support for CGM adoption. Session content and strategies are outlined in Table 3. Sessions target four primary topics. Each participant will receive content in the same order, but the program is designed to be flexible depending on individual barriers and concerns. Some participants may spend more time on certain topics than others. ONBOARD will approach CGM data interpretation

Table 3. ONBOARD Intervention Topic Content			
Barrier addressed	Topic name	Strategies used	Goals
	Introduction	- Psychoeducation; rapport building	
 - Provide rationale for ONBOARD - Introduce concepts from Technology Acceptance Model to discuss CGM pros and cons
Physical	Wearing Diabetes Device(s)	- Experiential wear	
 - Troubleshooting device placement - Provide education and examples of problem solving for common concerns and strategies for navigating them: appearance, insertion, skin irritation, discomfort, interference with daily activities - Provide resources for adhesive, skin prep, and adhesive removal

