2.7. Data analysis plan

Our team has extensive experience in the use of web-based assessment, data management and data analysis. Quantitative data will be entered into an online encrypted, HIPAA-compliant data management system, REDCap, with secure access for unique study IDs assigned to each participant. REDCap survey data is then ready for download by study staff and will be imported into SPSS for data cleaning and analysis. CGM data will be downloaded via Dexcom Clarity and LibreView which create a CSV file for transfer to REDCap and data analysis programs.

Demographic, medical, psychosocial variables, and some outcome measures are surveys and multi-item scales that participants will answer in REDCap. Psychometric properties of scales will be assessed before proceeding to investigate the proposed aims. These psychometric properties include item-total correlations and Cronbach's α to assess reliability. Total scores and subscale scores, when available, will be calculated and used for statistical analyses. Descriptive statistics will calculate frequencies, means and standard deviations for study variables. Independent samples t-tests and χ^2 analyses will assess potential differences between groups at baseline in demographic, psychosocial and diabetes variables. Analyses for Hypotheses 1&2 will follow the intention-to-treat principle.

To test Hypotheses 1&2, we will first conduct a treatment group comparison (ONBOARD vs. CGM-only) of the change in A1c, the primary outcome, from baseline to 3, 6, and 12 months. Specifically, we will use linear mixed models to model changes in A1c as a function of time, intervention assignment, and group-by-time interaction. These models will include a subject-specific random effect to account for the correlation of

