outcomes over time within a subject. We will examine change from baseline for each outcome as the dependent variable. We will begin by fitting models with minimum covariates prior to considering additional covariates. Similar models will be used to examine secondary outcomes of time in range, days of CGM wear (Hypothesis 1), diabetes distress, and perceived CGM benefit (Hypothesis 2). We will reference information criteria (e.g., Akaike's) to inform model selection decisions. Beyond testing the groups-by-time interaction term, custom contrasts will assess group differences at each time point. Exploratory analyses will examine differences between subgroups over time after primary, intent-to-treat analyses are completed. Additional exploratory analyses will examine patient-level predictors of CGM wear (e.g. age, gender, diabetes duration). For the CGM-continuer subgroup, we will conduct exploratory longitudinal analyses using CGM data to look at changes in time in range. We will adjust for multiple comparisons by using the Benjamini-Hochberg procedure and a false discovery rate of 0.05 (78). Analyses will initially be conducted without imputation for missing values, using the missing-at-random approach (79) and then multiple imputation will be used to supply values for missing data. We will conduct sensitivity analysis by multiple imputation to compare the effects.

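### The CGM system, chosen by the participant before randomization, is neither a stratum nor a prespecified covariate for the sensor-derived secondary outcomes

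*Combined protocol and SAP*

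**What the plan says.** Section 2.2 of the combined protocol and SAP: "Participants will be given the choice of using Dexcom G6 or Libre 2 CGM". The chosen supplies are mailed and started at the baseline visit. The section then says "At baseline, participants will then be randomized", and on the scheme "We will randomize at a 1:1 ratio, intervention to control". No stratification factor is named there or elsewhere.

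Section 2.7: "CGM data will be downloaded via Dexcom Clarity and LibreView which create a CSV file" for analysis. The primary model is to "model changes in A1c as a function of time, intervention assignment, and group-by-time interaction", with a subject-specific random effect, and the dependent variable is change from baseline. It continues: "Similar models will be used to examine secondary outcomes of time in range, days of CGM wear (Hypothesis 1". On covariates it says: "We will begin by fitting models with minimum covariates prior to considering additional covariates". None is named, and information criteria guide model selection. Device appears in no model, subgroup or sensitivity analysis.

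Section 2.3, on CGM use after the 12 supplied weeks: "After that time period, they can continue or discontinue use of CGM". Nothing says that those who continue keep the same system.

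**The concern.** Time in range, time below and above range, variability and wear are all read from the sensor, so the system worn is part of how they are measured. Because participants pick the system, it may also mark differences between the people who wear it.

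The protocol's own survey (section 1.3.2) gives a reason to expect some relation with wear. Among adults who had stopped CGM, 32.1% cited too many alarms, 30.1% inaccuracy and 28.1% discomfort or pain. Systems could differ on such features, although the documents do not compare these two.

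Device choice is therefore a plausibly prognostic variable, known for everyone before allocation, that the plan does not use. Three things are at stake for the Hypothesis 1 sensor outcomes:

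- some lost precision;
- an arm contrast that is harder to interpret if the device mix happens to be unequal;
- a device adjustment that, if made, would be decided after seeing the data.

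**Working it through.** **The plan's own figure.** Section 2.7 gives power only for A1c: above 0.80 at d = .35 with 89 per arm and autocorrelation .50. Averaging three follow-ups scales the SD by √((1 + 2 × 0.5)/3) = 0.816. Power is then Φ(0.35/0.816 × √(89/2) − 1.96) = Φ(0.90) = 0.816 (two-sided 0.05 assumed), so the figure reproduces. The plan gives no effect size or power for time in range or wear.

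**Inputs.** From section 2.7: n = 76 per arm after 15% attrition. Assumed, because the documents are silent: minority-device share p = 0.2 to 0.5, and between-device difference D = 0.1 to 0.5 within-device SD.

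**Chance imbalance without stratification.** SE of the gap in device share = √(2p(1 − p)/n).

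- p = 0.2: √(0.32/76) = 0.065, 95% limit ±12.7 points; a gap of 10 points or more in 12% of trials.
- p = 0.5: √(0.50/76) = 0.081, 95% limit ±15.9 points; a gap of 10 points or more in 22% of trials.

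**Shift in the arm difference** = gap × D.

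- 95% limit: 0.127 × 0.1 = 0.013 SD up to 0.159 × 0.5 = 0.079 SD.
- Typical size (mean absolute gap = 0.80 × SE): 0.80 × 0.065 × 0.1 = 0.005 SD up to 0.80 × 0.081 × 0.5 = 0.032 SD.

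**Gain from adjustment.** R² = p(1 − p)D²/(1 + p(1 − p)D²). An unadjusted power of 80% becomes Φ(2.802/√(1 − R²) − 1.96).

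- p = 0.2, D = 0.1: R² = 0.0016/1.0016 = 0.2%; power 80.1%.
- p = 0.5, D = 0.5: R² = 0.0625/1.0625 = 5.9%; power 82.3%.

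**Bias and type I error.** The unadjusted comparison was simulated 20,000 times per setting, with 76 per arm, p = 0.3 or 0.5 and D = 0.5 or 1.0 SD (the latter a stress value outside the range above). The mean arm difference was within 0.003 SD of zero, and overall type I error was 0.048 to 0.051. Only in trials with a device gap of 10 points or more did it rise: to 0.063 to 0.068 at 0.5 SD, and to 0.089 to 0.098 at 1.0 SD.

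**Levels or change.** These figures treat the device difference as present in the analysed outcome. The plan analyses change from baseline, and a constant offset cancels if the baseline value comes from the same system. Whether it does is unclear. Table 4 marks CGM measures at month 0, but section 2.2 lists downloads only at 3, 6 and 12 months, section 2.5 has participants begin CGM at baseline, and no run-in is described. For wear, cancellation would not remove a device difference that arises after CGM is started. The figures are therefore upper values within the assumed ranges.

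**The case against.** The strongest reply is that randomization already deals with this. Device is fixed before allocation, its variance is inside the outcome SD, and chance imbalance is ordinary sampling error already covered by the standard error. The same could be said of age, pump use or diabetes duration, and no figure in the documents shows that device matters more. The named primary endpoints, A1c from a mailed kit and diabetes distress, are not sensor-derived. The plan also leaves room for additional covariates.

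Most of this stands. A reader might infer that pooling two systems biases the trial's result; the order of events in section 2.2 and the simulation contradict that through week 12. Nor can one say that adjustment is ruled out. The accurate statement is that none is prespecified.

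What remains is that an open covariate clause combined with selection by information criteria is not a plan for device. Conditional on a visible imbalance, the unadjusted test is no longer at its nominal level, and any adjustment introduced then would be post hoc. Naming the covariate now avoids that.

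**Conclusion.** The point holds as a low-cost improvement to the analysis of secondary outcomes, not as a threat to the trial's main conclusions. Under the assumed device share and device difference, the arm contrast for a sensor outcome could shift by about 0.01 to 0.08 SD at the 95% limit, and adjustment is worth at most about two points of power. Both are smaller if a constant offset cancels in change from baseline. The sample size is unaffected.

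Two stronger readings should be resisted.

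- A reader might combine a 50/50 split at 89 per arm (95% limit 14.7 points) with a 0.8 SD device difference, giving 0.118 SD, and call it a third of the planned d = .35. No device difference is given in the documents, and d = .35 is the A1c effect, not a target for time in range or wear.
- A reader might infer that device switching after week 12 distorts the 6- and 12-month results. Protection is weaker then, because use is optional and the device mix among those still providing data could differ by arm. As an illustration, a 10- to 20-point gap with a 0.25 to 0.5 SD offset gives 0.10 × 0.25 = 0.025 to 0.20 × 0.5 = 0.10 SD. But the documents give no evidence that switching or differential retention by device will occur, so this is something to report, not a demonstrated bias.

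**What to change.** In section 2.7, prespecify the device chosen before randomization (Dexcom G6 or Libre 2) as a fixed covariate in the models for time in range, time below and above range, variability and wear. Use that choice throughout, not the system worn later. If enrolment has not begun, also stratify the 1:1 randomization by it; otherwise the covariate alone suffices.

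Tabulate the system in use at 6 and 12 months by arm, taken from whether the export came from Clarity or LibreView. Do not plan an inferential analysis that excludes participants who switch. Switching happens after randomization and may be influenced by ONBOARD, so any such display should be labelled descriptive only.

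The cost is one model term, a two-level stratum where still possible, and one table. It needs no additional participants and no new baseline data, since the mailed device is known.
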